## **5 Study Drug**

N/A

## **6 Study Procedures**

### Feasibility and Yoga Treatment Arm

Subjects will participate in two 75 minute sessions per week for the duration of radiation treatment with a yoga instructor offered for free by Patient Family Services in the Perelman Center of Advanced Medicine. Numerous sessions will be offered each week. Each session will begin with breathing and centering techniques (taking inventory of the levels of energy, posture, stress level, emotions, and breath). Yoga poses will consist of the following and can be modified based on patient needs: Sitting on chair: neck and shoulder series (neck and shoulders side, front and back movements, shoulder rolls, and arms movement), Table pose with opposite arm and leg movement. Side bent. Simple chair twist. Standing poses: Mountain pose, Warrior II series, Half Moon variation at the wall, Front warrior series, forward stretch/ bend variation with a chair. Recline poses will include: inverted lake pose (legs up the wall with a blanket for support), bridge pose variation, recline/ sided bound angle pose, modified Camel pose at the wall, modified Shoulder stand (legs up the wall with block support), reclining big toe posture with a belt, and corpse pose (Savasana – final rest). Modifications can and will be made based on

each subjects specific needs and physical restrictions. Poses will be added progressively. Not all poses will be done each session. Additionally subjects will fill out 4 types of QOL forms at various points during the study. The first is to be completed prior to start of radiation treatment, bi-weekly during treatment and within a week of the last yoga class or by the end of radiation

### No Yoga Treatment Arm

Control patients who are randomized to standard of care will not undergo any yoga intervention or participate in any structured yoga program during the study duration. They will undergo cancer and side effect treatment per standard of care, and they will be asked to complete all study-related questionnaires at the same time points as the patients in the yoga treatment arm.

## **7 Statistical Plan**

### **7.1 Design**

This is a feasibility study followed by a seamless transition to a randomized phase II study.

#### **7.1.1 Pilot study**

Feasibility (aim 1) will be declared if we successfully accrue 15 evaluable patients of the first 75 approached. Patients participating in the feasibility portion of the study will move seamlessly into the phase II study. The data from these patients will be included in the phase II trial portion of this study. Given the number of prostate cancer patients historically treated in the Radiation Oncology department, we anticipate that this rate of enrollment would allow completion of the phase II trial within <3 years.

#### **7.1.2 Randomized phase II trial**

##### **7.1.2.1 Sample size determination**

Our goal is to estimate effect sizes for a larger study. We are setting our recruitment aim for phase 2 up to 48 subjects, a 20% increase from our target enrollment in order to account for potential subject drop out and arrive at N = 40. Inclusion of subject data from

the feasibility portion results in  $N = 55$  up to  $N = 63$  should subject attrition levels prove lower than expected. Two groups (35 v 20) give us power to estimate an effect size for yoga participation with a 95% confidence interval that is approximately 1.1 standard-deviations wide (compared to the SD of the raw measure). For the corresponding caregivers, two groups (20 v 20) give power to estimate a CI that is 1.3 SD wide. The effect will be measured as a time x treatment interaction (difference of difference scores). From our own preliminary data, and from Hwang et al. (2008), we know that the within subject correlation for fatigue measures is approximately 0.5, and that the SD for the difference score will be similar to that of the raw measure at individual time points. For the time x treatment interaction, we will be able to detect a standardized effect size of  $d=0.7$  (0.8 for caregivers) at  $\alpha=0.05$  (one-sided) with 80% power.

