### Study Summary

Title	A Feasibility Study Followed by a Randomized Phase 2 Study of Yoga for Radiation Therapy Side Effects in Prostate Cancer
Short Title	Yoga for Prostate Cancer
Protocol Number	UPCC# 05813
Phase	Feasibility study followed by a randomized Phase II study
Methodology	A single arm pilot followed by a 2-arm study
Study Duration	12 months for Feasibility. 36 months for Phase II
Study Center(s)	Perelman Center for Advanced Medicine
Objectives	The purpose of this study is to ascertain the feasibility of yoga interventions as well as the effect of yoga on radiation-related fatigue, sexual dysfunction and urinary incontinence in patients with non-metastatic prostate cancer.
Number of Subjects	63
Diagnosis and Main Inclusion Criteria	Non-metastatic prostate cancer patients undergoing radiation therapy
Study Product, Dose, Route, Regimen	N/A
Duration of administration	Twice weekly yoga sessions for duration of radiation treatment.
Reference therapy	N/A
Statistical Methodology	The primary hypothesis will be tested using a two-group t-test to compare difference scores between Yoga and control groups.

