### **3.3 Study Endpoints**

#### **3.3.1 Pilot Study**

The primary goal of this pilot is to determine the feasibility of recruiting and retaining men into a clinical trial of yoga to improve fatigue and health related quality of life in prostate cancer patients undergoing radiation treatment. The endpoint is the number of evaluable patients accrued, with a minimum target goal of 15 of the first 75 eligible patients approached.

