## **4.5 Early Withdrawal of Subjects**

### **4.5.1 When and How to Withdraw Subjects**

The principal investigator may withdraw subjects if it is felt to be necessary for the health and safety of the subject. Additionally subjects may be withdrawn for not following study instructions. We expect up to 20% of subjects to drop out from the study due to time constraints, use of other CAM, and concurrent illness.

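### The phase II recruitment aim of 48 leaves about 38 patients, not 40, at the plan's own 20% dropout ceiling; the effect on power and precision is small

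*Combined protocol and SAP*

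**What the plan says.** Section 7.1.2.1 states the phase II target as follows: "We are setting our recruitment aim for phase 2 up to 48 subjects", which it explains as "a 20% increase from our target enrollment in order to account for potential subject drop out and arrive at N = 40". Adding the pilot patients gives N = 55, rising to 63 "should subject attrition levels prove lower than expected". The stated precision and power rest on 35 v 20 patients (95% confidence interval about 1.1 SD wide, d = 0.7) and 20 v 20 caregivers (1.3 SD, d = 0.8), with a one-sided alpha of 0.05 and 80% power.

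Section 4.5.1 gives the dropout assumption: "We expect up to 20% of subjects to drop out from the study".

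The pilot contribution is defined in two places. Section 7.1.1 says: "Feasibility (aim 1) will be declared if we successfully accrue 15 evaluable patients of the first 75 approached". Section 3.3.1 says: "The endpoint is the number of evaluable patients accrued, with a minimum target goal of 15 of the first 75 eligible patients approached".

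The Study Summary row "Number of Subjects" gives 63, without saying whether these are men enrolled or men analysed.

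**The concern.** An allowance for dropout has to be taken from the number recruited, because that is the group from which people drop out. Adding 20% to the number wanted at the end is a different and smaller allowance. If 20% of those recruited are lost, the plan does not reach the 40 it names, so the 35 v 20 and 20 v 20 on which the power and interval widths rest are not reached either. The stated design sits at almost exactly 80% power, so it has no slack to absorb a shortfall. The stated aim is to estimate effect sizes for a larger study, which makes the analysed N and the interval width what this phase is meant to deliver.

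A related ambiguity affects 63. It is the sum of a count before dropout (48) and a count after losses (15), so it is not cleanly an enrolment total or an analysed total.

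**Working it through.** **Inputs.** Recruitment up to 48, target 40, groups 35 v 20 and 20 v 20, d = 0.7 and 0.8, one-sided alpha 0.05, SD of the difference score about equal to the raw SD (section 7.1.2.1); dropout up to 20% (section 4.5.1); 15 evaluable pilot patients (sections 3.3.1 and 7.1.1). Equal allocation in phase II is inferred from 20 v 20.

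**1. Reproduce the plan's counts.** 40 x 1.2 = 48; 40 + 15 = 55; 48 + 15 = 63. All are exact.

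**2. Reproduce the plan's power and precision.** In SD units the standard error of the group difference is sqrt(1/n1 + 1/n2). The normal interval width is 2 x 1.96 x SE, and t-test power comes from the noncentral t distribution.
- 35 v 20: SE = sqrt(1/35 + 1/20) = 0.280. Width 1.10 SD (t: 1.12). Power at d = 0.7 is 80.3% (normal) or 79.4% (t). Detectable d by the t-test is 0.706.
- 20 v 20: SE = sqrt(1/20 + 1/20) = 0.316. Width 1.24 SD (t: 1.28). Power at d = 0.8 is 81.2% (normal) or 79.9% (t).

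The stated figures are therefore right for the group sizes they assume. The question is only whether recruitment delivers those sizes.

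**3. Apply the dropout ceiling to those recruited.**
- 48 x (1 - 0.20) = 38.4, about 19 per arm.
- Loss that 48 can absorb: 1 - 40/48 = 16.7%.
- Recruitment needed for 40 after a 20% loss: 40/(1 - 0.20) = 50.
- Pooled total: 38.4 + 15 = 53.4, about 34 v 19, against the stated 55.

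**4. Recompute at those sizes.**

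| Comparison | Power, t-test | Power, normal | 95% CI width, normal / t |
|---|---|---|---|
| Patients 35 v 20, d = 0.7 (stated) | 79.4% | 80.3% | 1.10 / 1.12 SD |
| Patients 34 v 19, d = 0.7 | 77.8% | 78.8% | 1.12 / 1.15 SD |
| Caregivers 20 v 20, d = 0.8 (stated) | 79.9% | 81.2% | 1.24 / 1.28 SD |
| Caregivers 19 v 19, d = 0.8 | 78.1% | 79.4% | 1.27 / 1.32 SD |

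The detectable d for 34 v 19 (t-test, 80% power) is 0.72. The caregiver row assumes that caregivers are recruited and lost at the same rates as phase II patients; the plan gives no separate caregiver recruitment figure.

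**5. Dependence on the dropout rate.** Treating losses as independent, the chance that at least 40 of 48 remain is 0.95 at 10% dropout, 0.71 at 15% and 0.36 at 20%.

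**The case against.** The 20% is a ceiling, not an expected rate. At 15% dropout, 48 recruited would more likely than not leave 40 or more, and at 10% they almost certainly would. Even at the ceiling, the loss is 1.6 percentage points of power for patients. By the normal formula the interval is still about 1.1 SD wide, a detectable d of 0.72 still rounds to 0.7, and the caregiver width still rounds to 1.3 SD. In a phase II study meant to inform a larger one, no decision turns on this. All of that stands, and it limits the size of the point. It does not make 48 the right figure, because a dropout allowance exists to cover the rate the plan names, and 48 does not cover it.

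Two stronger readings are tempting, and the documents support neither.

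- A reader might infer that the 15 pilot men are also counted without any dropout, so that 55 is overstated a second time. Sections 3.3.1 and 7.1.1 define the 15 as evaluable patients, so that count is already net of losses, and adding it undiminished to the post-dropout 40 is correct.
- A reader might take 63 as a cap on enrolment and remove 20% of everyone: 63 x 0.8 = 50.4 analysed against 55, about 31 v 19, with t-test power near 77%. No section calls 63 a cap. Section 7.1.2.1 presents it as the N reached if attrition is low. Section 7.1.2.3 defines evaluability by attendance at yoga sessions, which is not the same as dropout, and no section sets the pilot's non-evaluable share at 20%.

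**Conclusion.** The inflation is wrong as written: at the plan's own ceiling the recruitment aim should be 50, and 48 leaves about 38. The consequence is about two men fewer in the pooled analysis (53.4 against 55), with power at d = 0.7 of 77.8% against 79.4%, a detectable d of 0.72 against 0.706, and an interval 0.02 to 0.03 SD wider. Caregiver power at d = 0.8 is 78.1% against 79.9%. These figures assume the full 20% loss, spread equally over the two arms, and exactly 15 evaluable pilot men. At dropout of 16.7% or less there is no expected shortfall.

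The 63 in the Study Summary is a separate, lesser matter of labelling. It mixes men recruited with men evaluable, and the documents do not say which it is meant to count. That calls for clarification; it does not show that the trial will fall well short of 55.

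**What to change.** In section 7.1.2.1, do one of the following:
- set the phase II recruitment aim at 40/(1 - 0.20) = 50 and keep the stated 40, 55, power and interval widths; or
- keep 48, restate the expected phase II number at 20% dropout as about 38 (19 v 19) and the pooled number as about 53 (34 v 19), and replace power, detectable d and interval widths with the recomputed values for patients and caregivers.

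In the Study Summary, say whether 63 counts men enrolled or men analysed, and preferably give both totals. If the enrolment total is to include pilot losses, state the assumption behind it. For example, if pilot non-evaluability equals the 20% dropout, 15/0.8 = 18.75, about 19 pilot men enrolled, which gives 48 + 19 = 67 or 50 + 19 = 69. Those totals should be labelled as resting on that assumption.

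The cost is two more recruits under the first option, or slightly less favourable stated power and precision under the second. Otherwise the change is protocol wording only.

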#### **7.1.2.2 Statistical Methods**

This randomized study is a two-arm longitudinal controlled trial of yoga as a means of reducing fatigue over the course of radiation therapy for prostate cancer, with measures taken prior to treatment, during treatment, and in follow-up. The analysis will include the initial subjects from the feasibility study as an addition to the treatment arm, and we will control for any differences between the feasibility group and the randomized treatment arm using indicators. The primary measure, and most secondary measures, are Likert-style summary scores on a 0-10 scale and will be treated as Gaussian. The exception is retention, which is a binomial count of those remaining enrolled to the end.

Prior to performing analyses, standard data cleaning procedures will be applied (e.g., checking for outliers and data entry errors, creating summary scores for analysis, and checking that analysis assumptions are met). The assumptions underlying the statistical methods will be examined through the use of standard tests of normality, and graphical displays (27). All analyses will be conducted using Stata software (Stata Corporation, College Station, TX).

We will calculate descriptive statistics for all variables in the study. For outcome variables, we will summarize by treatment group (Yoga versus control) and by time point. We will also estimate correlations within subject for each of the study measures taken at different times.

The primary outcome for the randomized, phase II study will be the difference score of BFI fatigue while undergoing radiation therapy minus BFI fatigue prior to radiation. The primary hypothesis will be tested using a two-group t-test to compare difference scores between Yoga and control groups. This will be a one-sided test with type-1 error at  $\alpha=0.05$ . Similar analysis will be conducted using BFI fatigue at follow-up versus pre-radiation, and for all of the FACT-G fatigue measures. We will test the difference using a one-sided z-test. The FACT-G analysis will be repeated for caregivers (Aim 4).

Effect sizes will be reported for all outcome measures as standardized differences. The effect size will reflect the time x treatment interaction, and the standard deviations will be adjusted for within-subject correlation to aid in designing a larger study.

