#### **3.3.2 Randomized Phase II Study**

##### **3.3.2.1 Primary Study Endpoints**

The primary goal is to determine the effect size of yoga on fatigue. The endpoint is the difference in BFI fatigue score between time points during radiation therapy and baseline prior to radiation.

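### The primary t-test on BFI change omits baseline BFI; at the plan's r of about 0.5 and equal SDs, adjusting for it would cut the variance by about 23% with no new data

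*Combined protocol and SAP*

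**What the plan says.** Section 7.1.2.2 defines the primary outcome as "the difference score of BFI fatigue while undergoing radiation therapy minus BFI fatigue prior to radiation" and gives the test: "The primary hypothesis will be tested using a two-group t-test to compare difference scores between Yoga and control groups". It is one-sided at 0.05. The Study Summary repeats the "two-group t-test to compare difference scores between Yoga and control groups".

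Section 7.1.2.1 says that the aim is to estimate effect sizes for a larger trial. One of its inputs is that "the within subject correlation for fatigue measures is approximately 0.5". A second input, on the spread of the change score, reads: "the SD for the difference score will be similar to that of the raw measure at individual time points". On group sizes the section says: "Two groups (35 v 20) give us power to estimate an effect size for yoga participation", with a 95% interval about 1.1 SD wide and 80% power at d=0.7.

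Section 7.1.2.2 adds the feasibility patients to the yoga arm and says "we will control for any differences between the feasibility group and the randomized treatment arm using indicators". That is the only adjustment named. The closing remark there about adjusting SDs for within-subject correlation concerns how effect sizes are reported, not the test.

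BFI is completed before radiotherapy (section 3.2, item 2), and controls complete the same questionnaires at the same times (section 6).

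**The concern.** A change score subtracts the whole baseline value, which amounts to fixing the baseline slope at 1. With equal SDs and a correlation of 0.5 the best slope is 0.5, so the change score carries baseline noise into the comparison. Estimating the slope removes it. In randomised arms the adjusted arm effect targets the same between-arm difference in change that section 7.1.2.1 sets out to measure.

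The interval around the effect size is the main product of this study, so avoidable width matters. The plan is also incomplete as a model: a two-group t-test has no place for the promised pilot indicator, so some regression is already implied but is not written down.

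**Working it through.** **Inputs.** From 7.1.2.1: r about 0.5, change SD similar to raw SD, 35 v 20 patients, d=0.7, one-sided alpha 0.05, 80% power. Assumed: equal SDs at baseline and on treatment, and one on-treatment BFI value. At r=0.5, equal SDs give a change SD of √(2(1−0.5)) = 1.0 raw SD, which agrees with the plan's statement. The randomised 20 v 20 is inferred: 35 v 20 less the 15 pilot patients.

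**Formulas** (units of raw variance, total N, f = √(1/n₁+1/n₂)):
- Change score: variance 2(1−r), df N−2.
- Baseline-adjusted: variance (1−r²)(1+1/(N−4)), df N−3. The second factor is the cost of estimating the slope.
- CI width = 2·t₀.₉₇₅·s·f, where s² is the variance above. Power comes from the noncentral t with noncentrality d/(s·f).

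**The plan's own figures first.** For 35 v 20, f = √(1/35+1/20) = 0.280. The change score has s=1, so power at 0.7 is 79.4% (80.3% by the normal approximation) and CI width is 1.12 SD (1.10 normal). The stated 80% and 1.1 SD reproduce. The caregiver figures (20 v 20, d=0.8, 1.3 SD) also reproduce: 79.9% and 1.28 SD.

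**Adding baseline BFI at r=0.5.** The change variance is 2(0.5) = 1.00. The adjusted variance is 0.75 × 52/51 = 0.765 for N=55 and 0.75 × 37/36 = 0.771 for N=40. The cut is therefore 23.5% and 22.9%.

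| Contrast | Analysis | Detectable d (80% power) | 95% CI width | Power at d=0.7 |
|---|---|---|---|---|
| 35 v 20 | change | 0.71 | 1.12 SD | 79% |
| 35 v 20 | adjusted | 0.62 | 0.98 SD | 88% |
| 20 v 20 | change | 0.80 | 1.28 SD | 70% |
| 20 v 20 | adjusted | 0.70 | 1.13 SD | 80% |

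Simulation (100,000 trials per setting) gives power of 79.4% and 87.8% for 35 v 20, and 70.1% and 79.5% for 20 v 20. The simulated variance cuts are 23.3% and 22.6%.

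**With the pilot indicator fitted.** The arm coefficient then compares randomised yoga patients with controls. In the 55-patient model (20 randomised yoga, 15 pilot, 20 control; slope factor 1+1/50, df 51), detectable d is 0.80 for the change score and 0.70 adjusted, with power of 70.5% and 80.3%. This is nearly the same as 20 v 20 alone.

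**Sensitivity to r (20 v 20, equal SDs).** At r=0.3 the cut is 33% (detectable d 0.95 to 0.77). At r=0.7 it is 13% (0.62 to 0.58).

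**Sensitivity to the SD ratio (20 v 20, r=0.5).** Let k be baseline SD divided by on-treatment SD. In units of on-treatment variance, the change variance is 1+k²−2rk and the adjusted variance stays at 0.771.
- k=0.8: change variance 1+0.64−0.80 = 0.84; cut 1−0.771/0.84 = 8%.
- k=1.2: change variance 1+1.44−1.20 = 1.24; cut 1−0.771/1.24 = 38%.

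**The case against.** **This is a preference, not a defect.** The change-score test is valid under randomisation, and section 7.1.2.1 sized the study for it with figures that reproduce. This stands. A reader might infer that the primary test is wrong; the documents support only that it is less precise than it could be.

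**The 23% is one point in a wide range.** This stands too. It needs r near 0.5 and equal SDs. At k=0.8 the change SD is √0.84 = 0.92 of the on-treatment SD, which still fits the plan's word for it, yet the gain is only 8%. At k=0.6 the change variance is 1+0.36−0.60 = 0.76, so adjustment would be marginally worse. The correlation is approximate and comes partly from a cited exercise study in breast cancer.

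**The fall from 80% to 70% power is a separate matter.** A reader might blame it on the missing covariate. It comes from fitting the pilot indicator, which reduces the contrast to about 20 v 20, and the plan does not say outright that the indicator enters the primary test. A regression of change on arm and indicator would carry it without baseline BFI.

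**Estimates can move as well as tighten.** The 15 pilot patients are not randomised. Section 7.1.2.3 also defines evaluability by yoga attendance, which can select yoga patients after randomisation. If the compared groups differ at baseline by b SD, the two estimators differ by (1−r)b: 0.15 SD for an assumed b of 0.3 at r=0.5. So the 35 v 20 gain is not guaranteed to be pure precision, and adjustment does not remove bias from pooling.

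**The on-treatment visit.** Section 3.3.2.1 refers to the "difference in BFI fatigue score between time points during radiation therapy and baseline prior to radiation" and names no single visit or summary. A reader might conclude that week 4 should be primary. The documents do not settle this: the week-4 symptom peak is stated under the IIEF and IPSS, and no available text fixes a BFI in that week. Part of section 3.2 after the BFI schedule is missing from the text available for this review.

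**Conclusion.** The point holds as a recommended efficiency improvement. Baseline BFI is available in both arms, the primary test does not use it, and at the plan's r with equal SDs its inclusion lowers the variance by about 23%. For the randomised patients this is worth about 10 points of power at d=0.7. Even then adjustment only just reaches d=0.7: the break-even r is 0.51 for 20 v 20 alone and 0.49 in the indicator model. The 35 v 20 gain (detectable d 0.71 to 0.62) holds only if pilot patients do not differ from randomised yoga patients.

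The direction is secure over r from 0.3 to 0.7 with equal SDs. The size is not, because the documents give neither the SD ratio nor a range for r.

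**What to change.** - **7.1.2.2 and Study Summary:** make the primary analysis a linear model of on-treatment BFI on arm, baseline BFI and the pilot-cohort indicator. Keep the change-score t-test as a sensitivity analysis.
- **7.1.2.1:** as a separate correction, restate precision for the arm contrast in that model, about 20 v 20. With change scores this is a detectable d of 0.80 and a CI width of 1.28 SD. With baseline adjustment it is about 0.70 and 1.13 SD. The present 0.7 and 1.1 SD belong to an unadjusted 35 v 20. Give the assumed r and SD ratio with a range.
- **3.3.2.1 and 7.1.2.2:** state one on-treatment BFI visit or summary before analysis. Whether that is a single week or a mean is the sponsor's choice.

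The cost is wording, one degree of freedom for the baseline slope (and one for the indicator, which is already promised), and a decision made before analysis. No new data or visits are needed.

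### Section 7.1.2.2 names a one-sided z-test after calling the secondary comparisons similar to the primary t-test, and does not say what it tests; on the likeliest reading the error is 5.3% to 5.4%, not 5%

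*Combined protocol and SAP*

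**What the plan says.** The fourth paragraph of section 7.1.2.2 (Statistical Methods) sets out the tests in this order:

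- Primary outcome, the BFI score during radiation minus the score before it: "The primary hypothesis will be tested using a two-group t-test to compare difference scores between Yoga and control groups". The error rate follows: "This will be a one-sided test with type-1 error at" 0.05.
- Secondary outcomes: "Similar analysis will be conducted using BFI fatigue at follow-up versus pre-radiation, and for all of the FACT-G fatigue measures".
- Next sentence: "We will test the difference using a one-sided z-test".
- Next sentence, on caregivers: "The FACT-G analysis will be repeated for caregivers (Aim 4").

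The z-test sentence gives no error rate, no variance estimate and no definition of the difference being tested. The first paragraph of the same section says the scores will be treated as Gaussian and singles out retention as a binomial count, for which no test is named. The Study Summary mentions only the t-test.

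Section 7.1.2.1 gives the planned sizes. For patients: "Two groups (35 v 20) give us power to estimate an effect size for yoga participation with a 95% confidence interval" about 1.1 SD wide. For caregivers: "two groups (20 v 20) give power to estimate a CI that is 1.3 SD wide". The same section states 80% power at one-sided 0.05 for a standardized effect of 0.7 (0.8 for caregivers).

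**The concern.** A z-test refers the statistic to the normal distribution, which is exact only when the SD is known. Nothing in the plan says it is known, so it will be estimated from the trial data. The statistic then follows a t distribution, whose tail beyond 1.645 holds more than 5%. Followed as written, the plan would test the secondary and caregiver comparisons at slightly more than the nominal rate.

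The wording also leaves two tests available for one comparison: the t-test, carried over by the word similar, and the z-test in the next sentence. A result that falls between the two cutoffs would be significant by one and not by the other. That choice should be closed before the data are seen.

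**Working it through.** **Inputs**

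- Patients: 35 v 20, so df = 35 + 20 − 2 = 53 with a pooled SD (section 7.1.2.1).
- Caregivers: 20 v 20, so df = 38 (section 7.1.2.1).
- SD of the difference score: 1 raw SD, since "the SD for the difference score will be similar to that of the raw measure at individual time points".
- One-sided error of 0.05. It is stated for the primary test, and I assume it carries over to the z-test sentence. The normal cutoff is 1.645.

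**Step 1: reproduce the plan's figures.** The standard error in SD units is √(1/n₁ + 1/n₂).

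- Patients: √(1/35 + 1/20) = 0.280. Normal power at 0.7 is Φ(0.7/0.280 − 1.645) = 80.3%. With the noncentral t it is 79.4%.
- Caregivers: √(1/20 + 1/20) = 0.316. Normal power at 0.8 is Φ(0.8/0.316 − 1.645) = 81.2%. With the noncentral t it is 79.9%.

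Both agree with the stated 80%. The 95% interval width is 2 × critical value × standard error:

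| Comparison | Stated | With z | With t |
|---|---|---|---|
| Patients, 35 v 20 | 1.1 | 1.10 | 1.12 |
| Caregivers, 20 v 20 | 1.3 | 1.24 | 1.28 |

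The patient figure fits either method. The caregiver figure rounds correctly only from t.

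**Step 2: true error of the z-test.** With an estimated pooled SD, the size is P(t_df > 1.645).

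| Comparison | df | True one-sided error | Excess (points) | t cutoff for 5% |
|---|---|---|---|---|
| Patients, 35 v 20 | 53 | 5.30% | 0.30 | 1.674 |
| Caregivers, 20 v 20 | 38 | 5.41% | 0.41 | 1.686 |

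If the recruitment ceiling were fully retained, the figures would be 5.26% (39 v 24, N = 63) and 5.34% (24 v 24). A simulated z-test with unpooled variances gives 5.35% at 35 v 20 and 5.40% at 20 v 20, so the choice of variance estimate hardly matters.

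**Step 3: effect of switching to t.** The size is exactly 5% under normality. At the plan's effect sizes, power goes from 80.2% (cutoff 1.645) to 79.4% for patients, and from 81.1% to 79.9% for caregivers. The effects detectable with 80% power under t are 0.706 and 0.801, against the stated 0.7 and 0.8.

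**The case against.** The strongest reply is that the sentence may not concern these outcomes at all. Its object is undefined, retention is a binomial outcome with no other test assigned, and a z-test for two proportions would be ordinary there. If that was the intent, the error-rate argument for the continuous scores falls away. This stands as an uncertainty, but it does not rescue the text. Retention is mentioned three paragraphs earlier, while the z-test sentence sits between two sentences about FACT-G. On either reading it needs correcting.

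It is also fair to say that similar does not mean identical, and that a plan may name a different test for secondary outcomes. So this is an ambiguity rather than a flat contradiction. The excess is slight, and section 7.1.2.1 gives estimation of effect sizes as the goal.

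A reader might infer more than the documents support:

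- *That the primary test is affected.* It is not. The t-test is named for it in both the Study Summary and section 7.1.2.2.
- *That every secondary comparison has 20 or fewer per arm.* Only the caregiver comparison is planned at 20 v 20. Patient comparisons are planned at 35 v 20, because the feasibility subjects join the yoga arm.
- *That the confidence intervals will be too narrow.* The sentence concerns a test, and nothing says the intervals use 1.96. The stated caregiver width points to t.
- *That the error climbs well above 5% as caregiver numbers fall.* At 10 v 10 it would be 5.87%, but that size is an assumption and appears nowhere in the plan.

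**Conclusion.** The point holds as a minor one. The section names two tests without saying which applies to the secondary difference scores, and by position the z-test does. Followed as written, that gives a one-sided error of about 5.3% for patients and 5.4% for caregivers in place of 5%. Only a result whose t-based p-value lies between 0.050 and about 0.053 (patients) or 0.054 (caregivers) would change, so few conclusions would.

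The figures assume normal scores (as the plan does), an estimated SD, the planned group sizes, a plain two-group comparison, and a nominal 0.05 for the z-test. They apply only if the sentence refers to the continuous scores.

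**What to change.** Replace the z-test sentence with a statement that the follow-up BFI, FACT-G and caregiver FACT-G difference scores are compared by the same one-sided two-group t-test, at the same error rate, as the primary outcome.

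If the z-test was meant for retention, move it next to the retention sentence, name the outcome and specify an exact test. A pooled two-proportion z-test does not hold its level exactly either. At 24 v 24 its one-sided size is 5.16% if true retention is 80% in both arms (in line with the plan's allowance of up to 20% dropout), and 5.57% if it is 50% (an assumption).

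The cost is one sentence. No change in sample size is needed. The 0.8 and 1.2 points of power given up by moving from z to t come only from the excess error.
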